## 2.14 Interim analysis

No interim analysis is planned for this study.

## 3 Sample size calculation

All sample size and power considerations are performed using EAST 6.

The sample size was calculated based on the phase III results of the MEASURE2 study, which used the same dose and loading regimen as will be applied in this trial. Under the assumption of 56.9% ASAS20 responders in the Secukinumab (delayed tapering) group and 27.0% in the placebo group, a sample size of 62 patients per group is required to have 90% power to show superiority of Secukinumab over placebo at a two sided  $\alpha=5\%$ .

For the comparison of the the early tapering group at week 16 vs. placebo, the same treatment effect is expected, leading to the same sample size. To compensate for some dropout and other protocol deviations, the sample size will be increased to 68 per arm. The total sample size of this trial will thus be 204. At the time of writing the amendment, about 190 patients have been recruited into this trial and it seems unlikely that a sample  $> 200$  can be recruited within reasonable time. With this sample size, the (newly introduced 190) comparison of pooled Secukinumab groups vs. placebo, the trial would still have almost 80 % (78%) power if the placebo response was somewhat higher (35%) than originally assumed.

## 4 Change to protocol specified analyses

Not applicable.

## 5 Appendix

### 5.1 Imputation rules

#### 5.1.1 Study drug

- Investigational treatment:
  - Secukinumab 150 mg s.c. injection provided in a 1 mL PFS (1 PFS for 150 mg dose).
- Reference treatment:
  - Secukinumab placebo (Placebo) s.c. injection provided in a 1 mL PFS.

#### 5.1.2 AE date imputation

The following table explains the notation used in the logic matrix. Please note that **missing start dates** will not be imputed.

	Day	Month	Year
Partial Adverse Event Start Date	Not used	MON	YYYY
Treatment Start Date (TRTSTD)	Not used	TRTM	TRTY

The following matrix explains the logic behind the imputation.

	MON MISSING	MON < TRTM	MON = TRTM	MON > TRTM
YYYY MISSING	NC Uncertain	NC Uncertain	NC Uncertain	NC Uncertain
YYYY < TRTY	(D) Before Treatment Start	(C) Before Treatment Start	(C) Before Treatment Start	(C) Before Treatment Start
YYYY = TRTY	(B) Uncertain	(C) Before Treatment Start	(A) Uncertain	(A) After Treatment Start
YYYY > TRTY	(E) After Treatment Start	(A) After Treatment Start	(A) After Treatment Start	(A) After Treatment Start

The following table is the legend to the logic matrix.

If AE end date is complete and AE end date < Treatment start date or AE end date is partial and AE imputed end date < Treatment start date, then AE start reference = min (informed consent date, earliest visit date from SV) Else if AE end date is partial, AE end date > = Treatment start date or AE is ongoing, then AE start reference = treatment start date.

Relationship	Time imputation
Before AE start reference	Partial date indicates AE start date prior to AE start reference
After AE start reference	Partial date indicates AE start date after AE start reference

Relationship	Time imputation	
Uncertain	Partial date insufficient to determine relationship of AE start date to AE start reference	
Imputation Calculation		
NC/Blank	No convention	
(A)	MAX(01MONYYYY, AE start reference+1 day)	
(B)	AE start reference+1	
(C)	15MONYYYY	
(D)	01JULYYYY	
(E)	01JANYYYY	
Complete date	No date imputation	
If time is captured for the study
 
Case1: if AE start date is not equal to AE start reference then do the following:
 
If minutes missing then AESTMF = M and time is imputed to hh:00
 
If minutes missing then AESTMF = H and time is imputed to 00:00
 
Case2: if AE start date = AE start reference then AESTMF = H and time is imputed to treatment start time + 1 hour

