#### Treatment arms

Patients will be randomized 1:1:1 to one of the following treatment groups:

- **Secukinumab - delayed NSAID tapering:** Secukinumab 150 mg s.c. at weeks 0, 1, 2, 3, 4, 8, 12, 16 and 20 with placebo injections at Week 5, 6, 7 and 17, 18, 19 to maintain the blind.
- **Secukinumab – early NSAID tapering:** Placebo at weeks 0, 1, 2, 3 to maintain the blind; followed by Secukinumab 150 mg s.c. at Week 4, 5, 6, 7, 8, 12, 16 and 20 with intermittent Placebo injections at week 17, 18, 19 to maintain the blind.
- **Placebo:** Placebo at weeks 0, 1, 2, 3, 4, 5, 6, 7, 8 and 12. After the Week 16 assessments of the secondary endpoint have been performed, these patients will receive Secukinumab 150 mg s.c. at weeks 16, 17, 18, 19 and 20.

The patients will be stratified at randomization according to their status of prior TNF $\alpha$  inhibitor exposure, i.e. TNF $\alpha$  inhibitor naïve patients or TNF $\alpha$  inhibitor inadequate responders (TNF $\alpha$ -IR). The only condition that will be placed on enrollment targets for each stratum is that no less than 60% (i.e. 114) of patients are TNF $\alpha$  inhibitor naïve, i.e., no more than 40% (i.e. 76) of patients are TNF $\alpha$ -IR. In theory the percentage of TNF $\alpha$  inhibitor naïve patients could reach 100%, although that is not anticipated.

For primary analysis both the secukinumab treatment arms will be pooled and compared against placebo.

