### 2.1.1 General definitions

**Study treatment:** Study treatment refers to:

- Investigational treatment: Secukinumab 150 mg s.c. injection provided in a 1 mL PFS (1 PFS for 150 mg dose).
- Reference treatment: Secukinumab placebo (Placebo) s.c. injection provided in a 1 mL PFS.

Two secukinumab arms will be pooled for the primary analysis and for specified secondary analysis.

**Study treatment start and end date:** Study treatment start date is defined as the first date when study drug is administered and recorded on the Dose Administration Record (DAR) CRF page. Similarly, study drug end date is defined as the last date when a non-zero dose of study drug is administered and recorded on the DAR CRF page.

**Study day:** Study day will be calculated as (event date – study drug start date + 1 day) for the safety analysis and (event date – randomization date + 1 day) for the efficacy analysis. For events prior to study drug start date or randomization date (e.g., an adverse event occurred before the start of first dose), study day will be negative and calculated as (event date – study drug start date) and (event date – randomization date) for safety and efficacy analysis respectively.

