Treatment Period 2 is a double-blinded treatment period starting from Week 16 post-dose till Week 20.

**Lost to follow up:** The patients whose study completion status is unclear because they fail to appear for study visits without stating an intention to withdraw. A patient should not be formally considered lost to follow-up until his/her scheduled end of treatment visit would have occurred.

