### **2.8.1 Adverse events (AEs)**

The crude incidence of treatment emergent adverse events (i.e. events started after the first dose of study treatment or events present prior to the first dose of study treatment but increased in severity based on preferred term, and events until 30 days for AE and SAE after last dose of study treatment) will be summarized by primary system organ class and preferred term.

The summaries will be presented separately by study periods i.e. week 1-16 and after week 16.

In addition, exposure time-adjusted incidence rates including 95% confidence intervals will be provided for the entire treatment period to adjust for differences in exposure. A graphical display of the crude rates and exposure-adjusted incidence rates will be presented for all AEs and serious AEs by system organ class. A graphical display of relative frequencies within system organ classes and relative risks, as appropriate, will be presented.

Adverse events will be summarized by presenting, for each treatment group, the number and percentage of patients having at least one AE, having an AE in each primary system organ class and having each individual AE (preferred term).

The most common adverse events reported (>1 % in any group for each preferred term in the SOC-PT table or > 1 % in any group) will be presented in descending frequency according to its incidence in total secukinumab group (combining all secukinumab treatment groups) starting from the most common event.

Summaries (crude incidences only) will also be presented for AEs by severity and for study treatment related AEs. If a particular AE 'severity' is missing, this variable will be listed as missing and treated as missing in summaries. If a subject reported more than one adverse event with the same preferred term, the adverse event with the greatest severity will be presented. If a subject reported more than one adverse event within the same primary system organ class, the subject will be counted only once with the greatest severity at the system organ class level, where applicable.

Separate summaries will be provided for

- adverse events suspected to be related to study drug by the investigator
- deaths
- adverse events leading to discontinuation
- adverse events leading to temporary dose interruption.

The MedDRA version used for reporting the study will be described in a footnote.

Follow-up period summaries will be done for all patients in follow-up.

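### SAP 5.1.2 has no reference date for the placebo arm's first secukinumab injection, so some partially dated adverse events that begin after the Week 16 switch are imputed into the placebo period

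*SAP*

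**What the plan says.** SAP 5.1.2 sets the reference date for a partial AE onset in two branches. If the event ended before treatment, "then AE start reference = min (informed consent date, earliest visit date from SV". Otherwise, where the end date is on or after treatment start, "or AE is ongoing, then AE start reference = treatment start date". SAP 2.1.1 fixes the meaning of that date: "Study treatment start date is defined as the first date when study drug is administered".

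Three rules of the 5.1.2 legend matter here:

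- Rule A (month known, day missing, at or after the start month): "MAX(01MONYYYY, AE start reference+1 day").
- Rule B (month missing, same year as treatment start): "AE start reference+1".
- Rule E (month missing, later year): 1 January of that year.

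On the placebo arm, the SAP's treatment-arm description says that after the Week 16 assessments "these patients will receive Secukinumab 150 mg s.c. at weeks 16, 17, 18, 19 and 20". The period definitions put the boundary at that dose: "Treatment Period 2 is a double-blinded treatment period starting from Week 16 post-dose till Week 20". For AEs, SAP 2.8.1 says: "The summaries will be presented separately by study periods i.e. week 1-16 and after week 16". Table 2-2 has explicit before-switch and after-switch rules for efficacy values and visit-based safety values. Section 5.1.2 does not mention the switch.

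**The concern.** The imputation rule and the reporting boundary do not refer to the same event. The rule asks whether an AE began before or after the first injection of any kind. The tables ask whether it began before or after the Week 16 dose, which in the placebo arm is the first exposure to secukinumab.

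Around the first injection, the SAP resolves an uncertain onset as on treatment (reference date plus one day). Around the placebo arm's first active dose, the same rules choose the earliest on-treatment date that the reported month or year allows, so the uncertainty is resolved as off secukinumab. At stake are events under secukinumab that are listed and counted as placebo events and that disappear from the after-Week-16 summary of switched patients.

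**Working it through.** The plan states no figure on this point, so there is none to reproduce. The check applies the printed rules.

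**Inputs.** The Week 16 injection is on Day 16 × 7 + 1 = 113 and the Week 20 dose on Day 141 (SAP Table 2-1). AEs are collected to 30 days after the last dose, i.e. to Day 141 + 30 = 171 (SAP 2.8.1). Arm size is about 190 / 3 ≈ 63.

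**Assumptions.** Start dates are spread evenly over the calendar, onset is uniform over the days considered, the event is ongoing or ends after treatment start, and period tables go by onset date. An event counts as moved back if its imputed date is on or before the Week 16 injection date.

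**Direction.** For an on-treatment event, rules A, B and E return the earliest on-treatment date compatible with what was reported. The imputed date cannot be later than the true one. Events can cross Week 16 backwards but never forwards.

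**Example.** Start 23 Jan 2018; switch 112 days later, on 15 May 2018.

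| True onset | Day missing | Month missing |
|---|---|---|
| 20 May (on secukinumab) | MAX(1 May, 24 Jan) = 1 May: placebo period | 24 Jan: placebo period |
| 5 June (on secukinumab) | MAX(1 June, 24 Jan) = 1 June: stays after the switch | 24 Jan: placebo period |

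**Share of true post-switch events moved back** (every start date over four years):

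| Onset window | Day missing | Month missing |
|---|---|---|
| Days 114-141 | 52% (0% to 100% by calendar day of the switch) | 96% |
| Days 114-171 | 25% (0% to 52%) | 92% |

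No event with only the day missing in a month after the switch month was moved. The month-missing events that stay are those where a new year begins between switch and onset, so that rule E returns a date after the switch.

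**Size per event.** One affected patient is at most 1 / 63 = 1.6 percentage points in a table row. This is an upper limit: the tables count patients with at least one event, so a row changes only if the patient had no such event already in that period.

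**Effect on the Weeks 1-16 comparison.** The rules apply to all arms, so post-Week-16 events in the secukinumab arms also move back. A simulation assumed 16-week incidence of any AE of 60% on placebo and 67% on secukinumab, close to the earlier trials in Protocol 3.6 (55.7% to 63.5% and, for 150 mg, 65.3% to 69.6%), with the secukinumab rate in both arms after Week 16. With 5% of dates lacking the day and 1% the month, the difference went from 6.9 to 6.8 points. With 20% and 5%, it went from 6.8 to 6.4. These missing-date rates are illustrative; the documents give none.

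**The case against.** The best counter-argument is that little depends on this. Safety is an exploratory, descriptive objective with no hypothesis test. Exposure-adjusted rates are also given for the entire treatment period. AEs are asked about at every visit and the data are queried, so partial dates should be few. All of this stands, and it limits the importance of the point.

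SAP 2.8.1 also leaves date algorithms to Programming Specifications, which are not among the documents. They might add a switch rule. But 5.1.2 already prints a complete rule, and a different one elsewhere would contradict it. The consent or earliest-visit branch does not help either, because it covers only events that ended before treatment.

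A reader might infer two stronger things. The first is that all partially dated post-switch events are moved back. The printed rules do not do that: with only the day missing, about three quarters of those in Days 114-171 stay in place. The second is that the placebo-controlled comparison is materially narrowed. That follows only if the placebo arm is viewed alone; the parallel shift in the secukinumab arms largely cancels it.

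**Conclusion.** The point holds in a limited form. As printed, SAP 5.1.2 misallocates a definable set of events in switched placebo patients: those with the day missing in the month of the Week 16 injection, and about 92% of those with the month missing. The direction follows from the rules alone. The percentages rest on uniform onset and apply only to events whose dates are partial. The number of such events cannot be derived and is probably small, and the influence on the Weeks 1-16 difference is minor. What remains is an attribution error, with events on secukinumab recorded under placebo, and it is cheap to remove.

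**What to change.** In SAP 5.1.2, for patients switched from placebo, add the date of the first secukinumab injection as a second reference. Apply it when the partial onset is compatible with onset after that injection and the recorded or imputed end date is not before it:

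- day missing: MAX(01MONYYYY, first secukinumab date + 1 day);
- month missing: MAX(01JANYYYY, first secukinumab date + 1 day).

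Flag these events in the listing, and show the period tables under both the present and the revised allocation.

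**Gain.** Assume onset uniform over Days 2-169, a mean AE duration of 14 days and recorded end dates. The post-switch share of onsets is 56 / 168 = 1/3. Misallocation under the present rule is then 26% × 1/3 ≈ 9% of day-missing events and 92% × 1/3 ≈ 31% of month-missing events. Under the revised rule it falls to about 5% and 8%.

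**Cost.** A few lines of SAP text and programming before database lock. The remaining error runs the other way: some long or ongoing events that truly began on placebo will be counted after the switch, about 5% / (2/3) ≈ 7.5% of day-missing and 8% / (2/3) = 12% of month-missing placebo-period events. Without the end-date check, about 13% of day-missing placebo-period events would move forward. The check is weaker when the end month is also missing, because the SAP then imputes a late end date.

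The rule should not be extended to the secukinumab arms, where it would take some true secukinumab events out of the placebo-controlled table. Restricting it leaves the backward shift in those arms only, a further reason to show both allocations.

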**Adverse Event End Date Imputation**

Imputed date = date part of original date, if complete date

Imputed date = min (completion/discontinuation visit date, DEC 31, date of death), if month is missing

Imputed date = min (completion/discontinuation visit date, last day of the month, date of death), if day is missing

**Adverse Event End Time Imputation**

If the AE end date is complete and time is captured in the study then:

**Case 1.** if AE end date is not equal to Treatment end date, then do the following:

if minutes missing then time is imputed to hh:00 if time missing then time is imputed to 00:00

**Case 2:** if AE end date = Treatment end date then time is imputed to treatment end time

If the AE end date is partial then end time is imputed to 00:00.

**Imputed Date Flag**

If year of the imputed date is not equal to YYYY then date flag = Y

else if month of the imputed date is not equal to MON then date flag = M

else if day of the imputed date is not equal to day of original date then date\_flag = D

else date flag = null

### Imputed Time Flag

If hours of the imputed time is not equal to hours of original time then time flag = H

else if minutes of the imputed time is not equal to minutes of original time then time flag = M

else time flag = null.

### 5.1.3 Concomitant medication date imputation

This algorithm is used when *event* is the partial start date of the concomitant medication.

The following table explains the notation used in the logic matrix. Please note that **missing start dates** will not be imputed.

	Day	Month	Year
Partial CM Start Date	Not used	MON	YYYY
Treatment Start Date (TRTSDT)	Not used	TRTM	TRTY

The following matrix explains the logic behind the imputation.

	MON MISSING	MON < TRTM	MON = TRTM	MON > TRTM
YYYY MISSING	(C2) Uncertain	(C1) Uncertain	(C1) Uncertain	(C1) Uncertain
YYYY < TRTY	(D) Before Treatment Start	(A) Before Treatment Start	(A) Before Treatment Start	(A) Before Treatment Start
YYYY = TRTY	(C2) Uncertain	(A) Before Treatment Start	(C1) Uncertain	(B) After Treatment Start
YYYY > TRTY	(E) After Treatment Start	(B) After Treatment Start	(B) After Treatment Start	(B) After Treatment Start

The following table is the legend to the logic matrix.

Relationship	
Before Treatment Start	Partial date indicates CMD start date prior to Treatment Start Date
After Treatment Start	Partial date indicates CMD start date after Treatment Start Date
Uncertain	Partial date insufficient to determine relationship of CMD start date relative to Treatment Start Date
Imputation Calculation	
(A)	15MONYYYY
(B)	01MONYYYY
(C1 or C2)	IF relative reference start = before treatment start THEN TRTSDT-1 ELSE IF relative reference start = '' THEN TRTSDT+1
(D)	01JULYYYY

(E)	01JANYYYY
-----	-----------

### Concomitant Medication End Date Imputation

If not ongoing then -

Imputed date = date part of CMENDTC, [if complete date](#)

Imputed date = min(completion/discontinuation visit date, DEC 31), if month is missing, [\(C2, D, E\)](#)

Imputed date = min(completion/discontinuation visit date, last day of the Month), if day is missing, [\(A, B, C1\)](#)

### Concomitant Medication Date Flag

If not a complete date then

Y - If year of the imputed date is not equal to YYYY else M – If month of the imputed date is not equal to MON else D.

#### 5.1.3.1 Prior therapies date imputation

Not applicable.

#### 5.1.3.2 Post therapies date imputation

Not applicable.

#### 5.1.4 Medical History date of diagnosis imputation

Completely missing dates will not be imputed. Partial dates of diagnosis will be compared to the treatment start date.

- If DIAG year < study treatment start date year and DIAG month is missing, the imputed DIAG date is set to the mid-year point (01JULYYYY)
- Else if DIAG month is not missing, the imputed DIAG date is set to the mid-month point (15MONYYYY)

If DIAG year = study treatment start date year and (DIAG month is missing OR DIAG month is equal to study treatment start month), the imputed DIAG date is set to one day before study treatment start date.

### 5.2 AEs coding/grading

Not applicable.

### 5.3 Laboratory parameters derivations

Not applicable.

### 5.4 Statistical models

Covariance (ANCOVA) model:

Endpoints with continuous data type expected to be normally distributed will be analyzed using an analysis of covariance (ANCOVA) model with treatment and baseline stratification factors, baseline weight and baseline value and as covariates. Confidence intervals for the difference between each dose of secukinumab and placebo will be calculated.

**SAS code for ANCOVA:**

```
proc mixed data=aaa;  
class TRT STRATA;  
model response = TRT STRATA WEIGHT BASE / s;  
lsmeans TRT / diff;  
run;
```

In addition, key secondary variables measured at all post baseline visits up to Week 20 will be analyzed using longitudinal mixed effects ANCOVA model with treatment, baseline stratification factor and analysis visit as factors; and weight, baseline value, treatment by visit and baseline by visit interactions as covariates. An unstructured covariance structure will be assumed for this model. The significance of the treatment effects for secukinumab regimens at different analysis visits will be determined from the pairwise comparisons performed between secukinumab regimens and placebo at the appropriate analysis visits.

**SAS code for mixed model:**

```
proc mixed data=aaa;  
class TRT USUBJID AVISITN STRATA;  
model CHG=TRT STRATA AVISITN WEIGHT BASE TRT*AVISITN BASE*AVISITN  
/ s ddfm=kr;  
lsmeans TRT*AVISITN / diff cl;  
repeated AVISITN / type=un subject=USUBJID;  
Run;
```

In case the MMRM model does not converge the following sequential steps will be used:

1. change ddfm=kr to ddfm=bw. If still no convergence, perform step 2.
2. change type=un to type=cs. If still no convergence, perform step 3.
3. remove covariates of the model based on the scenario.

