Intra-articular corticosteroids are not permitted within the 4 weeks preceding randomization and up to Week 12. After Week 12, no more than 1 joint per 24-week period may be injected. No single injection should exceed 40 mg of triamcinolone (or equivalent) and the total dose of intra-articular corticosteroid may not exceed 80 mg of triamcinolone (or equivalent) during any 20-week period. Injection of intra-articular steroids is not permitted within 8 weeks prior to Week 20.

Non-steroidal anti-inflammatory drugs (NSAIDs) (including COX-1 or COX-2 inhibitors), low strength opioids and acetaminophen/paracetamol

Patients regularly using NSAIDs, low strength opioids, or paracetamol/acetaminophen should be on stable dose for at least 2 weeks before randomization to allow inclusion. They should remain on a stable dose in the study up to Week 4.

Changes in the NSAID intake will be captured by the patient in the patient diary and checked and be transferred into the eCRF at all scheduled study visits after week 4.

Patients taking low strength opioids or paracetamol/acetaminophen PRN within the 2 weeks before randomization can continue to do so in the study; however, they have to refrain from any intake during at least 24 hours before a visit with disease activity assessment.

After Week 12 assessments are completed, a change in the low strength opioids, or paracetamol/acetaminophen treatment regimen is permitted.

Any change of the low strength opioids, or paracetamol/acetaminophen treatment during the trial should be recorded on the appropriate Prior and Concomitant medication eCRF page.

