Week	-10 to -4	-4 to -2	BSL	1	2	3	4	5	6	7	8	12	16	17	18	19	20	F24
Adverse events/SAEs (if applicable, including injection site reactions) ⁷	X																	
NSAID intake reported in eCRF		Χ	Х	Х	Х	Х	Х											X
Provide NSAID Diary to patient and instruct patient							Х				Х	х	Х					
NSAID intake captured in patient diary								х	х	Х	Х	х	Х	х	Х	х	Х	
Check NSAID diary									Х		Х	Х	Χ				Χ	
Patient's global assessment of disease activity (VAS)			x	х	X		x		x		X	X	X				X	х
Patient's assessment of back pain intensity (VAS)			х	х	х		х		Х		Х	х	Х				Х	х
BASFI			Х	Х	Х		Х		Х		Х	Х	Х				Х	Х

	Scree	ning ¹																
	Screening Visit 1	Screening Visit 2		Treatment 1										Follow Up				
Week	-10 to -4	-4 to -2	BSL	1	2	3	4	5	6	7	8	12	16	17	18	19	20	F24
BASDAI			Х	Х	Х		Х		Х		Х	Х	Х				Х	Х
Spinal mobility (BASMI Linear + chest expansion)			х		Х		х				х	х	х				Х	
SF-36			Х				Х					Х					Х	
ASAS Health Index			Х				Х					Х					Х	
Erythrocyte Sedimentation Rate (ESR)		Х	х		Х		х				Х	х	х				Х	х
High sensitivity C-reactive protein (hsCRP)		Х	х		Х		Х				х	х	х				Х	х
HLA-B27			Х															

¹ If the patient's washout period ≤ 4 weeks, Screening visit 1 (SV1) and Screening visit 2 (SV2) can be performed on the same day.

² Eligibility and relevant medical history assessments are conducted at SV1, SV2 and Baseline (BSL) / Day 1'. The data for all three visits should be recorded on the corresponding eCRFs available at SV1.

³ The following eCRFs are to be completed: AS Disease background eCRF, Modified New York criteria for AS eCRF

⁴ These assessments are source documentation only and will not be entered into the eCRF.

⁵ The PPD skin test can be performed at any time during the Screening period, but it must be read within 72 hours and before randomization.

	Scree	ening ¹																
	Screening Visit 1	Screening Visit 2					Treat	tment	:1					Tre	eatment	2		Follow Up
Week	-10 to -4	-4 to -2	BSL	1	2	3	4	5	6	7	8	12	16	17	18	19	20	F24

⁶ A chest X-ray or MRI is required if it was not performed and evaluated within 3 months prior to Screening. The X-ray should be performed after it is certain the patient meets inclusion/exclusion criteria in order to minimize unnecessary exposure to radiation. The X-ray may be replaced by an MRI assessment.

⁷ AEs/SAEs occurring after the patient has signed the informed consent must be captured on the appropriate eCRF page. SAEs must be recorded from signing of informed consent, AEs must be captured from the BSL visit on.

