Response at Week 16 to ASAS20 for Secukinumab (early-tapering) versus placebo will be evaluated using a logistic regression model with treatment as a factor and baseline weight as a covariate.

ASAS-NSAID at Week 12

Between-treatment differences in the change in ASAS-NSAID relative to baseline will be evaluated using a mixed-effect model repeated measures (MMRM). Treatment group and analysis visit as factors, baseline ASAS-NSAID and weight as continuous covariates. Treatment by analysis visit and baseline ASAS-NSAID by analysis visit will be included as interaction terms in the model. An unstructured covariance structure will be assumed for the model. The significance of the Secukinumab pooled treatment effect will be determined from a linear contrast comparing the (mean of the) two Secukinumab regimens to placebo. The significance of the two individual Secukinumab treatment group effects will be determined from the pairwise comparisons performed between Secukinumab regimens and placebo.

BASDAI at Week 12/16

The change from baseline to Week 12/16 in total BASDAI will be analyzed using a MMRM with treatment regimen and analysis visit as factors and weight and baseline score as continuous covariates. Treatment by analysis visit and baseline by analysis visit will be included as interaction terms in the model. An unstructured covariance structure will be assumed for this model. The significance of the Secukinumab treatment effect will be determined from the pairwise comparisons performed between Secukinumab regimens and placebo.

Other secondary variables

SF-36 PCS

For the change in SF-36 PCS, between-treatment differences will be evaluated using a mixed effect repeated measures model (MMRM). Treatment group and analysis visit will be included as categorical factors and baseline SF-36 PCS score and weight as continuous covariates. Treatment by analysis visit and baseline SF-36 PCS score by analysis visit will be included as interaction terms in the model. An unstructured covariance structure will be assumed for the model. The significance of the Secukinumab treatment effect will be determined from the pairwise comparisons performed between Secukinumab regimens and placebo.

Between-treatment comparisons for binary variables in the FAS population (e.g. ASAS20) at individual analysis visits will be evaluated using a logistic regression model with treatment as a factor and weight as a covariate for any analysis up to end of study.

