### **ASAS-NSAID at Week 12**

Between-treatment differences in the change in ASAS-NSAID relative to baseline will be evaluated using a mixed-effect model repeated measures (MMRM). Treatment group and analysis visit as factors, baseline ASAS-NSAID and weight as continuous covariates. Treatment by analysis visit and baseline ASAS-NSAID by analysis visit will be included as interaction terms in the model. Initially an unstructured covariance structure will be assumed for the model. The significance of the Secukinumab pooled treatment effect will be determined from a linear contrast comparing the (mean of the) two Secukinumab regimens to placebo. The significance of the two individual Secukinumab treatment group effects will be determined from the pairwise comparisons performed between Secukinumab regimens and placebo.

Refer to Appendix section 5.1 for calculation of ASAS-NSAID scores.

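### If the ASAS-NSAID repeated-measures model fails to converge, the SAP's fallback to compound symmetry would understate the Week 12 standard error in confirmatory tests, provided Weeks 1–4 are in the model

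*SAP*

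**What the plan says.** - **Covariance.** For ASAS-NSAID, Protocol 9.5.1 states: "An unstructured covariance structure will be assumed for the model". It names no fallback. SAP 2.7.2 words the same item as: "Initially an unstructured covariance structure will be assumed for the model".
- **Fallback.** SAP 5.4 gives three steps on non-convergence: "change ddfm=kr to ddfm=bw. If still no convergence, perform step 2"; then "change type=un to type=cs. If still no convergence, perform step 3"; then "remove covariates of the model based on the scenario". The SAS code has no option for empirical standard errors.
- **Visits.** SAP 5.4 applies the model to "variables measured at all post baseline visits up to Week 20". The ASAS-NSAID paragraph in SAP 2.7.2 lists no visits.
- **NSAID dosing and data.** Protocol 5.5.7 says of patients regularly using NSAIDs: "They should remain on a stable dose in the study up to Week 4". In Protocol Table 6-1 the row "NSAID intake reported in eCRF" is marked at baseline and Weeks 1, 2, 3 and 4. Diary capture follows from Week 5, and the diary is checked at Weeks 6, 8, 12, 16 and 20.
- **Role of the tests.** H2 (pooled arms), H7 and H8 (single arms) compare the Week 12 change in ASAS-NSAID with placebo. H2 is tested second, and H3 to H11 are confirmatory only if it is rejected.

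**The concern.** Compound symmetry fits one variance for all visits. If four early visits have almost no spread and Week 12 has an SD near 40, the common variance lies well below the Week 12 variance, and so does the standard error of the Week 12 contrast.

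The same feature of the data, near-zero early variance, can also make the unstructured fit fail. Step 1 cannot repair this: moving from Kenward–Roger to between-within changes the degrees of freedom and the small-sample adjustment, not the likelihood being maximised. Compound symmetry is therefore the first step that acts.

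At stake are the error rate of H2, which gates nine later hypotheses, and the width of the confidence intervals for the NSAID-sparing effect. Step 3 adds a choice of covariates that is open after the data are seen.

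**Working it through.** **Inputs from the documents.** About 190 patients, randomised 1:1:1 (SAP 1.1); two-sided 5%; ASAS-NSAID reductions of 63.9 and 36.6 (difference 27.3) with SD 40, and 62 per group (Protocol 9.7).

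**Assumed.** SDs at visits other than Week 12, dropout (10%, simulation only) and the share of patients changing NSAID dose by Week 4. The documents give none of these.

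**1. The plan's own figure.** SE = 40 × √(2/62) = 7.18; 27.3/7.18 − 1.96 = 1.84; power = 96.7%. The stated figure of over 90% is reproduced.

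**2. Can the unstructured fit fail?** Suppose a share q of patients makes one lasting dose change by Week 4, spread evenly over the four visits. If nobody new changes before a given visit, that visit's scores repeat the previous visit's (or are all zero), and the matrix is singular. Approximately,

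P(singular) = 1 − [1 − exp(−190q/4)]⁴.

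- q = 2%: exp(−0.95) = 0.387, so P = 86%
- q = 5%: exp(−2.375) = 0.093, so P = 32%
- q = 10%: exp(−4.75) = 0.0087, so P = 3%

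Simulation agrees: 100% at q = 0.5%, then 86%, 32% and 3% at these three values, 0.3% at 15% and 0% at 20%.

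**3. What compound symmetry does to Week 12.** With treatment-by-visit and baseline-by-visit terms and near-complete data,

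SE ratio r = √(mean visit variance / Week 12 variance); actual α = 2[1 − Φ(1.96 r)].

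| Visits and assumed SDs | Mean variance | r | α |
|---|---|---|---|
| Weeks 1–4: 0; Weeks 6–20: 40 | 8000/9 = 888.9 | 0.745 | 14.4% |
| Weeks 1–4: 5; Week 6: 25; Week 8: 35; then 40 | 6750/9 = 750 | 0.685 | 18.0% |
| Weeks 1–4: 20; Week 6: 30; Week 8: 35; then 40 | 8525/9 = 947.2 | 0.769 | 13.2% |
| Week 4: 5; Week 6: 25; Week 8: 35; then 40 | 6675/6 = 1112.5 | 0.834 | 10.2% |
| Week 6: 25; Week 8: 35; then 40 (no Weeks 1–4) | 6650/5 = 1330 | 0.912 | 7.4% |
| Weeks 8–20: 40 throughout | 1600 | 1.000 | 5.0% |

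**4. Simulation under the null.** There were 1,500 runs with 190 patients, the SAP's visit and baseline terms, and a REML compound-symmetry fit. Monte Carlo SE at 5% is √(0.05 × 0.95/1500) = 0.6 points.

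- Early SD 5: r = 0.68; H2/H7/H8 type I error 18.9/18.7/18.1%.
- Early SD 15: r = 0.73; 14.9/14.5/15.5%.
- Post-Week-4 visits only, SD still rising: 7.8–8.3%. With equal SDs from Week 8: 5.0–5.3%.
- Equal SDs at all visits with autoregressive correlation: 5.1–5.5%. The harm therefore comes from unequal variances, not from the correlation pattern.
- For the two early-SD settings, compound symmetry with a sandwich standard error gave 4.8–5.9%. A Week 12 ANCOVA, standing in for a structure with its own Week 12 variance, gave 4.6–5.8%.

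**The case against.** The strongest reply is that the fallback may never be used, and much of it stands.

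- **Frequency.** A reader might infer that failure is likely. The documents do not support that. They give no adherence figure, and SAP 5.6 has a deviation code for unstable NSAID dosing up to Week 4 that keeps such patients in every analysis. At about 10% changers or more, singularity is rare. A singular matrix is also only a stand-in for the SAP's trigger; no SAS convergence check was run.
- **Visits.** That Weeks 1–4 enter the model is an inference. The all-visits wording in SAP 5.4 is about key secondary variables, and SAP 2.6 says there are none. Against this, section 5.4 holds the only MMRM fallback in the plan, and SAP 2.7.2 implies for ASAS-NSAID that the unstructured form is only a starting point.
- **Familywise error.** A reader might infer that the 5% control is broken outright. It is not. The 13–19% applies only when step 2 is used. If that happens with probability π, overall error for the test is roughly π × α(CS) + (1 − π) × 5%, and π is unknown. If the true difference is near the planned 27.3, a valid test would very probably reject too.
- **BASDAI.** A reader might extend the point to H3 and H9–H11, which share the ladder. Nothing holds BASDAI fixed early, so there is no comparable reason for non-convergence, and any inflation figure would rest on assumed early SDs. That extension should not be made.

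The objection does not remove the defect: a written rule, followed as written, can give a wrong standard error in a gating test.

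**Conclusion.** The point holds as a conditional one. If the ASAS-NSAID model includes Weeks 1–4 and step 2 is used, the Week 12 standard error is about 0.7 of the true value and type I error about 13–19%. Nominal 95% intervals would then cover about 81–87% under the same conditions. If only Week 4 of the early visits is included, the error is about 8–10%; with post-Week-4 visits alone, about 5–8%.

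These sizes rest on the protocol's SD of 40 at Week 12 and on assumed SDs elsewhere. The chance that the fallback is used runs from near zero to near certain with adherence to stable dosing, so no unconditional error rate can be given beyond saying that it is lower. The SAP should be changed because the remedy is specific and nearly free, not because failure has been shown to be probable.

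**What to change.** In SAP 2.7.2 and 5.4:

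1. State that the ASAS-NSAID MMRM uses Weeks 6, 8, 12, 16 and 20, the assessment visits after tapering is allowed. This removes the near-zero-variance visits.
2. Replace step 2 with a fixed order of heterogeneous-variance structures: TOEPH, then ARH(1), then CSH. Require empirical (sandwich) standard errors for any structure other than unstructured. This is still needed after item 1, because compound symmetry gave about 8% while the SD was still rising at Weeks 6–8.
3. Replace the open wording of step 3 with a fixed order of covariate removal.

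The cost is a few lines of text and code, and slightly less efficient standard errors if the fallback is used. Under item 1, patients with no ASAS-NSAID value from Week 6 onward drop out of this model (Protocol 9.4.3 removes those without post-baseline values). Their early change scores would carry little information about Week 12, but their number should be reported.
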